11 STATISTICAL ANALYSIS

11.1 Pharmacokinetic population

Data from subjects who provide evaluable pk profiles for both Test and Reference products will be included in the pk and statistical analysis for bioequivalence determination. Subjects that are non-evaluable for a particular study period (or treatment in this case, as the study is a two-way crossover) are:

- Subjects with a pre-dose concentration greater than 5% of the C_{max} value for the subject in that period.
(Note that if a pre-dose concentration of etoricoxib in Period 1 or 2 is detected but is equal to or less than 5% of the C_{max} value for the subject in that Period, the subject's data will be included in the pk and statistical analysis without adjustment).
- Subjects presenting no measurable concentrations or only very low plasma concentrations for the Reference product (i.e. AUC_{0-72h} (or AUC_{0-t} if applicable) is less than 5% of the Reference product geometric mean AUC_{0-72h} (or AUC_{0-t} if applicable), which should be calculated without inclusion of data from the outlying subject): These subjects will be excluded from the pk and statistical evaluation. However, an additional statistical evaluation including such subjects will be performed and presented in the Statistical Report.
- Subjects who experienced any circumstance(s) that could imply that the plasma concentration-time profile is unreliable (i.e. due to AEs, concomitant medications, violation of study restrictions, missing pk samples): In these cases, decisions on the non-inclusion of these subjects in the pk and statistical analysis will be made by the Sponsor prior to the start of the bioanalysis. In case of missing pk samples, subjects will be only excluded from both pk and statistical analysis when there are more than 2 consecutive missing samples along the concentration-time profile. However, a sensitive analysis (bioequivalence assessment) will be performed including these subjects.

Although not included in the statistical BE assessment, pk parameters of non-evaluable subjects as per criteria mentioned above will be calculated if enough data are available and will be presented separately.

Samples from drop-out/withdrawal subjects will be assayed; however, subjects who do not provide evaluable data for both Test and Reference products (according to the above mentioned criteria), will not be included in the statistical analyses for BE determination and will be presented separately. If there are enough data available, pk parameters will be calculated for these subjects and will be presented separately.

In cases where concentrations of etoricoxib cannot be determined due to bioanalytical or clinical reasons, these values will be set to missing (no value) for the pk analysis.

Below LLOQ (Lower Limit of Quantification) concentrations will be treated as zero for all statistical analyses.

Any decision for excluding data from the final data set will be provided with a detailed explanation and will be properly recorded and dated.

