#### Effects of other drugs on the pharmacokinetics of etoricoxib

The main pathway of etoricoxib metabolism is dependent on CYP enzymes. CYP3A4 appears to contribute to the metabolism of etoricoxib in vivo. In vitro studies indicate that CYP2D6, CYP2C9, CYP1A2 and CYP2C19 also can catalyse the main metabolic pathway, but their quantitative roles have not been studied in vivo.

**Ketoconazole:** Ketoconazole, a potent inhibitor of CYP3A4, dosed at 400 mg once a day for 11 days to healthy volunteers, did not have any clinically important effect on the single-dose pharmacokinetics of 60 mg etoricoxib (43% increase in AUC).

**Voriconazole and Miconazole:** Co-administration of either oral voriconazole or topical miconazole oral gel, strong CYP3A4 inhibitors, with etoricoxib caused a slight increase in exposure to etoricoxib, but is not considered to be clinically meaningful based on published data.

**Rifampicin:** Co-administration of etoricoxib with rifampicin, a potent inducer of CYP enzymes, produced a 65% decrease in etoricoxib plasma concentrations. This interaction may result in recurrence of symptoms when etoricoxib is co-administered with rifampicin. While this information may suggest an increase in dose, doses of etoricoxib greater than those listed for each indication have not been studied in combination with rifampicin and are therefore not recommended.

**Antacids:** Antacids do not affect the pharmacokinetics of etoricoxib to a clinically relevant extent.

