14. Use of any enzyme-modifying drugs, including strong inhibitors of cytochrome P450 (CYP) enzymes (such as cimetidine, fluoxetine, quinidine, erythromycin, ciprofloxacin, fluconazole, ketoconazole, diltiazem and Human Immunodeficiency Virus (HIV) antivirals) and strong inducers of CYP enzymes (such as barbiturates, carbamazepine, glucocorticoids, phenytoin and rifampicin) within 30 days prior to Day 1 Period 1.
15. Use of Over the Counter (OTC) medications within 7 days prior to Day 1 Period 1. It will be specifically reminded that this includes cold preparations, acetylsalicylic acid (ASA), natural products used for therapeutic benefits and antacid preparations.
16. Intake of any prescription medication within 30 days prior to Day 1 Period 1.
17. Maintenance therapy with any drug or significant history of drug dependency.
18. Alcohol abuse, i.e. regular use of more than 10 units per week (one unit of alcohol equals 250 mL of beer, 125 mL of wine or 25 mL of spirits), a history of alcoholism or recovered alcoholics.
19. Positive alcohol, drugs of abuse or cotinine results at screening (Day -1).
20. Positive result on Day -5 and/or Day -2 of screening on COVID-19 RT-PCR test.
21. History of drug abuse or use of illegal drugs: use of soft drugs (e.g. marihuana) within 6 months of screening or hard drugs (e.g. amphetamines, barbiturates, benzodiazepines, cannabinoids, cocaine and opioids) within 1 year of screening.
22. A positive Human Immunodeficiency Virus antibody (HIV-Ab) screen, Hepatitis B surface antigen (HBsAg) or Hepatitis C Virus (HCV) tests.
23. Use of an investigational product within 60 days prior to Day 1 Period 1 or active enrolment in another drug or vaccine clinical study.

24. Use of depot injectable solutions with a half-life of >1 week within 6 months prior to Day 1 Period 1.
25. Subjects previously randomised in this study.
26. An inability to follow a standardised diet and meal schedule or inability to fast, as required during the study.
27. Donation of blood (at least 100 mL) or plasma by plasmapheresis within 30 days prior to Day 1 Period 1.
28. Volunteers who report difficulty swallowing tablets as a whole.

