### **8.3. Discontinuation Criteria**

Subjects will be allowed to discontinue their participation from the study at any time for any reason. A subject may also be discontinued to protect their health or the integrity of the study if necessary. The reason, date and time of withdrawal or termination will be documented in the subject's Case Report Form (CRF) and in the Clinical Study Report (CSR).

Subjects will be withdrawn from the study for any of the reasons below:

- A positive result to alcohol test performed at screening on Day -1.
- A positive result to drugs of abuse tests performed at screening on Day -1.
- A positive result to cotinine test performed at screening on Day -1.
- A positive result to COVID-19 RT-PCR test on Day -5 and/or Day -2 of screening.
- Clinically relevant SBP, DBP or HR readings outside the normal ranges on Day -3 or prior to study drug administration on Day 1 Period 1, as deemed by the Investigator. SBP, DBP and HR normal ranges are 90 to 140 mmHg, 60 to 90 mmHg and 50 to 100 beats/min, respectively.
- Forehead body temperature readings outside the range of 35.5 to 37.4 °C on Day -1 or prior to study drug administration on Day 1 Period 1.
- A subject who experiences emesis and/or severe diarrhoea within 2 hours (2 times expected median  $t_{max}$ ) after study drug administration.
- Subject leaves the CU during confinement.

Subjects may also be withdrawn by the Principal Investigator (PI) or Co-Investigator for any of the following reasons:

- Significant AEs that could interfere with subject's safety.
- Significant protocol violations.
- Difficulties with blood collection.
- Subject is uncooperative during the study.
- Use of concomitant medications which at the Investigator's discretion, are reasonably likely to interfere with the study medication and may put the subject at risk.
- Intercurrent illness that can affect the BA of the study drug or may put the subject at risk.
- If the PI judges it is in the subject's best interest.

Subjects discontinuing the study after first dosing will not be replaced.

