##### **8.4.1. Concomitant Medication**

Subjects must not take any medication (including OTC) until the end of confinement. Should a subject take any concomitant medication after first drug administration, it will be at the Investigator's (or delegate) discretion to decide whether the volunteer should remain in the study, depending on the drug used, the time of drug intake, etc. The drug name, time of drug intake and dose administered must be recorded.

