### **13.6. Adverse Event Collection**

The period of observation for collection of AEs extends from the screening until the FU visit (incl. washout period) for each subject. Any AEs occurring within this period will be recorded in the CRF.

At least the below details in relation to AEs will be reported by the Investigator:

- Description of the event
- Onset of the event (date and time)
- End of the event (date and time)
- Seriousness
- Severity
- Relationship with study drug (causality assessment)
- Last study drug administered prior to AE occurrence (incl. date and time)
- Action taken
- Outcome

The Sponsor will code all reported AEs by System Organ Class (SOC) and Preferred Term (PT) using the current version of the Medical Dictionary for Regulatory Activities (MedDRA). MedDRA coding of all reported AEs will be included in the CSR. AEs occurring after the subject signs ICF but before the first administration of IMP will be reported separately from those occurred after the first IMP administration.

It is the Investigator's responsibility to ensure that subjects who experience any AE receive appropriate follow up and treatment when required. Every action taken as a consequence of an AE must be appropriately documented.

In cases where there is any open AE after the FU visit, every effort should be made to follow the AE to resolution, give a reasonable explanation for its persistence, or to report it is mild and safely resolving.

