7 STUDY DESIGN

This is an open-label, two-period, two-sequence, two-way crossover, randomised, single dose bioequivalence study in healthy male volunteers under fasting conditions. Treatment periods will be separated with a washout period of at least 14 days.

Each study subject will be randomly assigned (in accordance with the Randomization List) to receive one FCT of either Test or Reference medication on Day 1 of each study period.

The following measures will be implemented to reduce bias:

- Subjects will be sequentially assigned to receive either Test or Reference product in a random fashion.
- Eligibility of subjects will be based on the fulfillment of all study inclusion and exclusion criteria.
- The Clinical Unit (CU) staff will monitor and record subject's compliance and any non-compliance with the protocol requirements.

The Bioanalytical Laboratory staff will not have access to the study Randomization List.

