8 JUSTIFICATION OF SAMPLE SIZE

Based on published data [5] [6] [7] [8], the highest intra-subject Coefficient of Variation (CV) following an oral single dose of etoricoxib 120 mg appears to be approximately 20% for C_{max} . Taking into account this value and assuming the a priori maximum difference of 5% between formulations, according to the approach of Zhang P [9] it is estimated that a sample size of 26 subjects in a two-period, two-sequence design should be sufficient to meet the bioequivalence (BE) range with a statistical a priori power of at least 90% with an alpha level protection of 0.05. Therefore, the inclusion of 28 subjects should be sufficient to also cover any potential drop-outs/withdrawals and variations around the estimated intra-subject CV.

To ensure that 28 volunteers are administered with the study medication, at least 2 standby subjects will remain at the CU until the last subject is dosed in the first study period.

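### The Sponsor decides, without treatment masking or fixed criteria, which subjects with AEs, concomitant drugs or violations leave the primary BE set

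*SAP*

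**What the plan says.** SAP 11.1 lists three classes of non-evaluable subjects, and protocol 15.2 has the same text. The first two (pre-dose concentration, very low Reference exposure) are numeric. The third covers any circumstance that could make a profile unreliable, with AEs, concomitant medication, restriction violations and missing samples as examples. For this class "decisions on the non-inclusion of these subjects in the pk and statistical analysis will be made by the Sponsor", before bioanalysis starts. Missing samples then get a fixed rule (more than two consecutive); the other three get none. The bullet ends with a sensitivity BE analysis that includes the excluded subjects.

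On masking, SAP 7 states: "This is an open-label, two-period, two-sequence, two-way crossover, randomised, single dose bioequivalence study". Only the bioanalytical laboratory is denied the randomisation list. The label segment placed on the CRF shows T or R (protocol 10.4, 11.3.2), each AE record names the last study drug given (13.6), and a monitor designated by the Sponsor reviews source documents (16.5). SAP 9 and SAP Appendix 1 print all 28 sequences.

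On drugs taken during the trial, exclusion criterion 14 covers enzyme modifiers, including "strong inducers of CYP enzymes (such as barbiturates, carbamazepine, glucocorticoids, phenytoin and rifampicin) within 30 days prior to Day 1 Period 1". That window ends at first dosing. After it, protocol 8.4.1 bars all medication, but the consequence of an intake is left to the Investigator's "discretion to decide whether the volunteer should remain in the study, depending on the drug used" and other factors.

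**The concern.** A rule that hides concentrations protects against selection only if the decision-maker cannot otherwise tell which way a case pushes T/R. Here the decision-maker can see the product, and for some events the protocol supplies the direction. Rifampicin "produced a 65% decrease in etoricoxib plasma concentrations" and ketoconazole raised AUC by 43% (both 5.2.5); food lowered Cmax by 36% (5.2.4). In a crossover, an event confined to one period affects one product in that subject, so it does not cancel.

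The party that decides has an interest in the result, and no criterion obliges it to treat a Test-period case and an identical Reference-period case alike. What is at stake is the T/R estimate and the 5% error level of the trial's one decision.

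**Working it through.** **Inputs from the documents.** 28 subjects, 14 per sequence (SAP 9); intra-subject CV 20% and a 5% formulation difference (SAP 8); 90% CI within 80.00–125.00% (protocol 15.4); effect sizes −65%, −36% and +43% as above.

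**Assumed, because the documents give no figure.** The number or rate of events, their equal likelihood under T and R, and worst-case selection.

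**The plan's own figure.** σ_w = √ln(1 + 0.20²) = 0.198 and SE = σ_w·√(2/n), with n − 2 degrees of freedom. The power of the two one-sided tests at a ratio of 0.95 is 89.6% for n = 24, 91.8% for 26 and 93.5% for 28. The smallest even n with at least 90% is 26, as stated. The sample size is not in question.

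**Shift from one affected subject.** The estimate of ln(T/R) is the average of the two sequence means of ln T − ln R. With 14 per sequence, one Test-period effect of factor f moves it by ½ × (1/14) × ln f = (ln f)/28; a Reference-period effect moves it by the same amount the other way.

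| Effect | (ln f)/28 | T/R factor, Test period | T/R factor, Reference period |
|---|---|---|---|
| −65% (f = 0.35) | −0.0375 | 0.963 | 1.038 |
| −36% (f = 0.64) | −0.0159 | 0.984 | 1.016 |
| +43% (f = 1.43) | +0.0128 | 1.013 | 0.987 |

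**False-BE rate at true T/R = 0.80, given that one event has occurred.** Simulated with the SAP's 2×2 contrast (400,000 trials per setting). With no event the rate is 5.0%.

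| Event | Test-period case kept | Reference-period case kept | Subject excluded |
|---|---|---|---|
| −65% | 0.4% | 9.5% | 5.0% |
| −36% | 2.3% | 7.7% | 5.0% |

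Averaging over an event equally likely under T or R:

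- Always keep: (0.4 + 9.5)/2 ≈ 4.9% for −65%; (2.3 + 7.7)/2 = 5.0% for −36%.
- Always exclude: 5.0% in both.
- Exclude Test-period cases, keep Reference-period cases: (5.0 + 9.5)/2 ≈ 7.2% for −65%; (5.0 + 7.7)/2 ≈ 6.4% for −36%.

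**Range over assumed event rates.** Let each subject-period have probability p of a −36% event. Dropping only subjects affected in the Test period gives 6.6%, 9.9% and 16.5% for p = 2%, 5% and 10%, with on average 0.5, 1.3 and 2.5 subjects dropped. For +43% events, dropping only subjects affected in the Reference period gives 6.5%, 8.8% and 13.8%. Keeping all affected subjects, or dropping all of them, stays between 4.9% and 5.1% throughout. The upper rates serve only to show the trend; nothing in the documents suggests they would occur.

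**The case against.** The case on the other side is substantial, and much of it stands.

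- **Timing is not the only safeguard.** A reader might infer that it is. In fact each exclusion must be explained, recorded and dated (SAP 11.1); all samples from dosed subjects are assayed (protocol 14.4); SAP Table 1 gives the reason for each exclusion; and Tables 4.2, 6.2 and 8.2 show the excluded subjects' data. An assessor could usually redo the analysis. These measures make selection visible; they do not prevent it.
- **A sensitivity analysis is planned.** Its wording can be read as covering the whole bullet. But the sentence directly follows the missing-samples rule, SAP 14 lists no output for it, and nothing says how a disagreement with the primary result is read.
- **Not every effect has a known direction.** A reader might infer that each does. Antacids have no relevant effect (5.2.5), food leaves extent unchanged (5.2.4), and most listed AEs have no stated effect on exposure.
- **The obvious AE example is largely covered.** Emesis or severe diarrhoea within 2 hours of dosing is a withdrawal criterion whichever product was given (protocol 8.3). Only later or milder events remain open.
- **Events should be rare.** Subjects are confined through washout, luggage is checked at admission, leaving the unit means withdrawal, and all medication is barred. A strong inducer is an extreme case.
- **The Sponsor does not yet know which limit is at risk.** Before bioanalysis, T/R is unknown and the assumed 5% difference has no stated direction. If the true ratio were 1.25, the same selection would lower the false-BE rate: by symmetry on the log scale, (0.4 + 5.0)/2 = 2.7% for a −65% event. The worst case assumes that the guess is right.

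**Conclusion.** The point holds as a gap in protection, not as a finding of bias. For AEs, concomitant drugs and violations there is no criterion and no masking, and the Test manufacturer decides. Given one event, the worst-case false-BE rate is about 7.2% (−65%) or 6.4% (−36%) against 5%. This rests on 28 subjects, CV 20%, true T/R 0.80, equal likelihood under T and R, and selection in the right direction. Unconditionally the excess is smaller, in proportion to how rarely such events occur.

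Two stronger readings are not supported. At a true ratio of 0.95, a trial with one Test-period profile reduced by 65% passes 67% of the time if the subject is kept and 93% if excluded. A reader might take that gap as the bias. It is power lost by keeping a corrupted profile, and a masked exclusion would recover it equally. A reader might also see a contradiction in protocol 8.3, where the concomitant-medication item requires interference and risk together while the intercurrent-illness item requires either. The two items concern different circumstances and the Investigator's withdrawal decision, so there is nothing to reconcile for this point.

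It is a cheap improvement worth making before bioanalysis starts.

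**What to change.** In SAP 11.1 and protocol 15.2:

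1. Take and sign these decisions before bioanalysis on a listing with treatment, sequence, period and subject number removed or recoded. The decision-maker should be existing staff who have not seen the randomisation list. Because the SAP prints the list, this rules out anyone holding the SAP, and subject number plus period would reveal treatment. The Sponsor may comment but not decide.
2. State evaluability criteria that apply identically whichever product was given, including for drugs in the exclusion criterion 14 classes taken after first dosing.
3. State that the sensitivity BE analysis includes every subject excluded under this bullet, not only those with missing samples. Add its output to SAP 14, reported beside the primary result.

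The cost is wording in two documents and one extra masked listing from data already collected. The downside is that a subject may be lost by rule whom the Sponsor would have kept. Sample size and study procedures do not change.

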11.2 Pharmacokinetic Study Variables

Etoricoxib plasma concentrations achieved by administering a single dose of study medication (T or R) will be measured to determine the pharmacokinetic profile of the Test product in relation to the Reference product.

The pk parameters that will be estimated are listed below:

11.2.1 Primary Variables

The main PK parameters of interest for this study will be C_{max} and AUC_{0-72h} .

C_{max} : Maximum observed plasma concentration, obtained directly from the data – without interpolation.

AUC_{0-72h} : Cumulative area under the plasma concentration time curve calculated from 0 to 72 hours, using the mixed model linear log trapezoidal rule. If there are concentrations below LLOQ (Lower Limit of Quantification) at 72 hours post-dose in at least one subject, then AUC_{0-t} will be calculated for all volunteers instead of AUC_{0-72h} .*

* AUC_{0-t} (if applicable): Cumulative area under the plasma concentration time curve calculated from 0 to the last observed concentration above Lower Limit Of Quantification (LLOQ), using the mixed model linear log trapezoidal rule.

11.2.2 Secondary Variables

t_{max} will be provided for information purposes only.

t_{max} : Time of maximum observed plasma concentration; obtained directly from the data, without interpolation. If it occurs at more than one time point, t_{max} is defined as the first time point with this value.

*The following PK parameters will be calculated only in the event that not all subjects have quantifiable concentration levels at 72 hours post-dose (in addition to AUC_{0-t} , C_{max} and t_{max}). They will be provided for information purposes only:

$AUC_{0-\infty}$: Area under the plasma concentration time curve extrapolated to infinity.

Residual area (AUC%extra or Extrapolated %AUC): Extrapolated area calculated as follows: $(AUC_{0-\infty} - AUC_{0-t}) / AUC_{0-\infty} * 100$.

$k_{el} (\lambda_z)$: Elimination rate constant.

$t_{1/2}$: Plasma half life, calculated as $0.693/k_{el}$.

11.3 Descriptive Statistics

The concentrations will be listed and described by formulation and theoretical time and the pharmacokinetic parameters will be listed and described by formulation.

The following descriptive statistics will be used: Mean, SD, Minimum, P25, Median, P75, Maximum, CV, 95% CI of Mean, Geometric Mean, SD (log), CV (Geometric Mean) and N.

Additionally the same listing and descriptive analyses will be performed separately for subjects not included in the statistical bioequivalence assessment (i.e. not included in the pharmacokinetic population, see section 11.1).

For C_{max} and AUC_{0-72h} (or C_{max} , AUC_{0-t} and $AUC_{0-\infty}$, if applicable) individual ratios (T/R) will be presented as part of the descriptive analysis.

